#### 9.1.10 Tumor Marker

PSA will be measured by a third-party organization according to a separately prepared written procedure. Progression of disease as indicated by PSA (based on the Prostate Cancer Handling Guidelines, 4th Edition [16]) is defined as an increase of at least 25% in the PSA value measured at least 4 weeks after the minimum PSA value measured during the study period (at least 12 weeks if the minimum value was recorded during screening). In such a case, the amount of increase must be at least 2 ng/mL. The date this condition is met will be considered the disease progression date.

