#### 9.3.1 Screening

Observations and tests will be performed within 28 days prior to the first dose of study drug to confirm subject eligibility for study participation based on the inclusion and exclusion criteria presented in Section 7.0. See Section 9.1.23 for the preparation of records for subjects withdrawing from the study during screening.

The following tests, observations, and assessments will be performed at screening.

- Informed consent
- Demographics, medical history, concurrent medical condition, treatment history
- Physical examination
- Vital signs
- Weight, height, and BMI
- ECOG performance status
- HBsAg, HCV, and HIV antibody and serologic test for syphilis  
If the institutional review board judges it necessary, these tests will be performed only for subjects determined by the investigator to be at high risk for hepatitis B or C or HIV infection.
- 12-lead ECG
- Chest X-ray examination
- Imaging assessments
- Clinical laboratory tests (hematology, chemistry, metabolic panel, and urinalysis)
- Cardiac tests
- Pharmacodynamic assessments (serum testosterone, LH, FSH, DHT, and SHBG)
- Tumor marker (PSA)
- Concomitant medications
- Concomitant therapies
- PTEs

The following tests will be performed only in Part B.

- Ophthalmological examinations
- Bone mineral density
- QOL assessments

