### **9.3.3 Day of Study Treatment Initiation**

The following tests, observations, and assessments will be performed before study drug is administered on the day of study treatment initiation. If 12-lead ECG or clinical laboratory tests were performed at screening up to 3 days prior to treatment initiation, then they may be used as the tests performed prior to treatment initiation.

- Physical examination
- Vital signs
- Weight
- 12-lead ECG
- Clinical laboratory tests (hematology, chemistry, metabolic panel, and urinalysis)
- Pharmacokinetic assessments

The following tests will be performed only in Part B

- Pharmacodynamic assessments (only serum testosterone by high-sensitivity measurement)
- BMP concentrations
- QOL assessments

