4.1 Efficacy Analysis

4.1.1 Antitumor Effects

Analysis Set:	Full Analysis Set		
Analysis			
Variable(s) :	(1) PSA (ng/mL)		
	(2) Rate of Progression Based on PSA (%)		
	(3) Rate of Progression Based on Imaging Assessments (%)		
Visit :	(1) Baseline, WK5D1, WK9D1, WK13D1, WK17D1, WK21D1, WK25D1,		
	WK37D1, WK49D1, WK61D1, WK73D1, WK85D1, WK97D1,		
	WK13D1 (LOCF), End of Study		
	(3) WK49D1, WK97D1		

Analytical

Method(s): The following analysis will be performed using the full analysis set.
(1) For the observed values, descriptive statistics and two-sided 95% confidence intervals of the mean will be provided for each visit by treatment group. Case plots as well as the mean and standard deviation plots of changes over time will be provided for each treatment group. The same analysis will be performed for the percent change from baseline.

The percent change from baseline at WK13D1 (LOCF) as well as the percent change from baseline when the PSA value is at its minimum since the start of the study drug administration will be shown using waterfall plots for each treatment group.

(2) Rate of progression based on PSA will be defined as the proportion of subjects who have a 25% or greater increase as well as an absolute increase of 2 ng/mL or more in the value of PSA at least 4 weeks from the nadir. If the value of PSA never decreased from baseline, the above conditions will be fit to the value obtained after WK13D1. A missing value will be assigned if neither of the following conditions is met: "there are at least two observations after study drug administration" or "there is at least one observation on or after WK13D1 and the baseline is not missing". If the same minimum PSA value occurs at several visits, then the PSA value with the earliest date will be used as the nadir. Frequency distributions will be provided for each treatment group.

(3) Rate of progression based on imaging assessments will be defined as the proportion of subjects who have developed new lesions. Frequency distributions will be provided for each visit by treatment group.

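### SAP 4.1.1 does not test a WK13D1 PSA for progression in Part B patients whose PSA never fell, although its own evaluability clause and Protocol 9.1.10 both admit that value (minor).

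*SAP*

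**What the plan says.** SAP 4.1.1 (Part B) defines PSA progression as a rise of at least 25% and at least 2 ng/mL, at least 4 weeks from the nadir. It reports the proportion of subjects who meet this, as frequency distributions by treatment group. For patients without any fall it adds: "If the value of PSA never decreased from baseline, the above conditions will be fit to the value obtained after WK13D1".

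The next sentence sets evaluability: "A missing value will be assigned if neither of the following conditions is met". The two conditions are "there are at least two observations after study drug administration" and "there is at least one observation on or after WK13D1 and the baseline is not missing". Either one is enough.

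Protocol 9.1.10 gives the same 25% and 2 ng/mL thresholds and the same 4-week interval, with a longer interval for a screening minimum: "at least 12 weeks if the minimum value was recorded during screening". Protocol 5.2.3 lists PSA-assessed progression as an additional endpoint of Part B.

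**The concern.** The clause that decides which value is tested says *after* WK13D1. The clause that decides whether the patient counts says *on or after* WK13D1. A patient can therefore be evaluable because of a WK13D1 value that the test does not use. The protocol's interval is inclusive and runs from the screening sample, and a WK13D1 value on schedule satisfies it.

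At stake is a PSA progression rate that may come out slightly too low, through patients whose PSA never responded. PSA progression is itself a lack-of-efficacy reason for withdrawal (Protocol 7.5), so a patient who qualifies at WK13D1 may leave before WK17D1.

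A second, lesser gap is that the two-observation condition is not restricted to patients who have a post-baseline nadir. A never-declining patient seen only at WK5D1 and WK9D1 passes it, although no value can be tested.

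**Working it through.** **Inputs.** Weeks 5, 9 and 13 fall on Days 29, 57 and 85 (Protocol 8.1.3.1). Screening runs from Day -28 to Day -1 and includes PSA (Protocol 9.3.1). Protocol 9.3.3 lists the assessments that "will be performed before study drug is administered on the day of study treatment initiation", and PSA is not among them. Table 9.c has 9 tumor-marker samples, which matches screening plus eight visits (WK5, 9, 13, 17, 21, 25, 37, 49). There is no Day 0, and the PSA window for WK13D1 is Days 71 to 98 (SAP, Definition of Visit Window). Part B has 15 subjects per group (Protocol 13.3).

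**Step 1: the visit day.** (13 − 1) × 7 + 1 = 85, which reproduces the stated Day 85.

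**Step 2: days since the baseline PSA.** For study day *d* and a screening sample on Day −*s*, the interval is (*d* − 1) + *s*, with *s* from 1 to 28. Twelve weeks is 84 days.

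| Sample | Study day | Days since baseline PSA |
|---|---|---|
| WK9D1 | 57 | 57 to 84 |
| First day of WK13D1 window | 71 | 71 to 98 |
| WK13D1 as scheduled | 85 | 85 to 112 |
| First day after WK13D1 window | 99 | 99 to 126 |
| WK17D1 as scheduled | 113 | 113 to 140 |

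A WK13D1 sample on Day 85 always reaches 84 days. Within the ±2-day visit allowance the only shortfall is Day 83 with a Day -1 baseline (83 days). Under the SAP wording the first scheduled value tested is WK17D1.

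**Step 3: the SAP clauses applied to a never-declining patient, scheduled visits only.**

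| PSA visits attended | Two or more values | Value on or after WK13D1 | Status | Tested under *after* | Tested under *on or after* |
|---|---|---|---|---|---|
| WK5 | no | no | missing | no | no |
| WK5, 9 | yes | no | non-missing | no | no |
| WK13 | no | yes | non-missing | no | yes |
| WK5, 9, 13 | yes | yes | non-missing | no | yes |
| WK5, 9, 13, 17 or further | yes | yes | non-missing | yes | yes |

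Of the 2^8 = 256 attendance patterns, five are non-missing with nothing to test: WK13; WK5+9; WK5+13; WK9+13; WK5+9+13. Changing *after* to *on or after* repairs all but WK5+9.

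**Step 4: the withdrawal PSA.** Protocol 9.3.7 requires one within 8 days. Read by date, a sample after WK13D1 can be tested. Read by window, a sample on Days 86 to 98 falls in the WK13D1 window, where the observation closest to Day 85 is used, so a WK13D1 sample taken on schedule displaces it. The End of Study visit keeps the last value, but SAP 4.1.1 lists that visit for PSA values and gives no visit list for the progression rate. The nadir tie rule ("then the PSA value with the earliest date will be used as the nadir") points towards dates without settling it.

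**Step 5: size.** The documents do not say how many patients are affected. As an assumption, take an arm of 15 with no other progression and 0 to 2 patients of each kind. Kind (a) qualifies at WK13D1 with no later qualifying value. Kind (b) has no value 84 days or more after baseline. As written, every case gives 0/15 = 0%.

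- One (a): 1/15 = 6.7%.
- One of each: 1/14 = 7.1%.
- Two of each: 2/13 = 15.4%.
- (b) alone: 0/14 or 0/13, still 0%.

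The denominators of 14 and 13 follow from setting (b) to missing.

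**The case against.** *After* may be deliberate. On windowed visits, values after WK13D1 start at Day 99 and always satisfy 12 weeks, whereas a Day 71 value inside the WK13D1 window may be only 71 days from baseline. This is a fair account of how the wording may have arisen. It does not remove the mismatch with the neighbouring clause, and it still discards an on-schedule value that meets the protocol.

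A missed progressor is hard to produce, and this largely stands. The patient must never decline, qualify at WK13D1 and have no later qualifying PSA. A never-declining patient who still qualifies at WK17D1 is caught one visit later, and a withdrawal sample will often be available. The Handling Rules for Analysis Data, which were not available for this review, may settle how that sample is used. They cannot be assumed to cure the wording.

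Setting never-declining patients to missing when nothing is testable is debatable. A patient whose PSA fell but who has equally short follow-up stays in the denominator, so the change removes only poor responders. This stands, and that part of the fix is therefore secondary.

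A reader might infer that the SAP declares untestable patients to be non-progressors. It does not say so. That follows only from the missing rule combined with a rate defined as a proportion of subjects.

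**Conclusion.** The point holds as a minor inconsistency. SAP 4.1.1 leaves untested a WK13D1 value that its own evaluability clause and Protocol 9.1.10 both admit. Any resulting error lowers the rate. One missed progressor is 6.7 percentage points in an arm of 15, but the number of such patients is unknown and may be zero. The two-observation gap changes only the denominator when no value lies 84 days or more after baseline.

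This rests on three things: the baseline PSA is the screening sample, untestable but non-missing patients remain in the denominator, and the Handling Rules do not override the SAP text.

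A reader might go further and conclude that the Part B PSA results in general are biased, or that a planned interval estimate is wrong. The documents support neither. By-visit PSA summaries and waterfall plots do not use this rule, and progression from a post-baseline nadir is still caught. SAP 4.1.1 plans only frequency distributions for this rate, with no confidence interval, in contrast to the castration rate in SAP 4.3.1.

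**What to change.** **Main change.** For patients whose PSA never fell below baseline, apply the 25% and 2 ng/mL criteria to any evaluable PSA dated at least 84 days after the baseline sample, including the withdrawal sample. Use actual dates, not windowed visits. Use the same condition in the evaluability clause.

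Writing *on or after WK13D1* in the test clause is not enough if visits are windowed. A Day 71 sample falls short of 84 days for any baseline from Day -13 to Day -1. The date rule also handles the reverse case, such as a WK9D1 sample exactly 84 days after a Day -28 baseline.

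**Secondary change.** Set progression to missing for a never-declining patient with no such value, and report how many there are. Keep the two-observation condition for patients whose PSA fell below baseline and for those without an evaluable baseline, so that no patient is left without a rule.

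**Cost.** SAP wording and minor programming. The rate may be slightly higher and its denominator slightly smaller.

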4.1.2 QOL Assessment

•	
Analysis Set:	Full Analysis Set
Analysis	
Variable(s) :	(1) AMS
	(2) EORTC-QLQ-C30
	(3) EPIC
Visit :	Baseline, WK5D1, WK9D1, WK13D1, WK21D1, WK25D1, WK45D1,
	WK49D1, WK61D1, WK73D1, WK85D1, WK97D1, SFU
Analytical	
Method(s):	The following analysis will be performed using the full analysis set. The
	scoring procedures are described in detail in the Appendix.
	(1) Descriptive statistics for the actual values and the percent change from
	baseline of AMS subscale scores and total scores will be provided for each
	visit by treatment group.
	(2) Descriptive statistics for the actual values and the change from baseline of
	Global health status/QoL score and each Functional scales score (physical,
	role, emotional, cognitive, social) will be provided for each visit by treatment
	group.
	(3) Descriptive statistics for the actual values and the change from baseline of
	each HRQOL Domain Summary Score (urinary, bowel, sexual, hormonal)
	will be provided for each visit by treatment group.

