**CONFIDENTIAL**

### 13.1.6 Other Analysis

[Other endpoints]

QOL assessment based on AMS, EORTC-QLQ-C30, and EPIC (Part B)

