### **13.3 Determination of Planned Sample Size**

[Part A]

Each cohort will have 3 or 6 subjects, based on the guidelines on the clinical evaluation of antineoplastics.

[Part B]

In order to detect less frequent AEs, 15 subjects per group (total of 30 subjects) were established as the number of cases enabling an approximately 80% chance of detecting AEs characterized by a true incidence of 10%.

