5.3.2 Vital Signs, Physical Findings, and Other Observations Related to Safety	
5.4 Displays of Treatment-Emergent Adverse Events (Japanese)	
6 Safety Analysis (Part B)	53
6.1 Treatment-Emergent Adverse Events	53
6.1.1 Overview of Treatment-Emergent Adverse Events	53
6.1.2 Displays of Treatment-Emergent Adverse Events	54
6.2 Pretreatment Events	56
6.2.1 Displays of Pretreatment Events	56
6.3 Laboratory and Other Safety Data	57
6.3.1 Laboratory Test Results	57
6.3.2 Vital Signs, Physical Findings, and Other Observations Related to Safety	60
6.4 Displays of Treatment-Emergent Adverse Events (Japanese)	62
7 Significance Level and Confidence Coefficient (Part A and Part B)	62
Amendment History	63
Appendix 1. Amendments from the Previous Version	1
Appendix 2. Criteria for Markedly Abnormal Values and Elevated Liver Enzyme	1
Appendix 3. QOL Scoring Procedures	1

Glossary

- Treatment-emergent adverse event (TEAE): An adverse event whose date of onset occurs on or after the start of study drug
- Descriptive statistics: number of subjects, mean, standard deviation (SD), maximum (max), minimum (min), and quartiles
- CV: coefficient of variation
- Randomized set: All subjects who were randomized. The first maintenance dose prescribed will be used as the treatment group when conducting analyses.
- Treatment group: For part A, the assigned cohort will be the treatment group. For part B, the first maintenance dose prescribed will be the treatment group.
- PK: pharmacokinetic
- MAV: markedly abnormal value
- ATC: anatomical therapeutic chemical
- LDH: lactic dehydrogenase
- GGT: gamma-glutamyl transpeptidase
- CK (CPK): creatine phosphokinase/kinase
- Study Day: The day before the first dose of the study drug will be defined as Study Day -1 and the day of the first dose will be defined as Study Day 1. If the date of the observation is on the same date or after the day of the first dose, Study Day will be calculated relative to Study Day 1. Otherwise, Study Day will be calculated relative to Study Day -1.
- Follow-up Day: The day after the last dose of the study drug will be defined as Follow-up Day
 1. Follow-up Day will be calculated relative to Day 1.

Definition of Visit Window

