Appendix 3. QOL Scoring Procedures

(1) AMS

AMS subscale scores and total scores will be calculated as follows. If one or more of the scores required for the calculation of a subscale are missing, then that particular subscale and the total score will be treated as missing.

- Psychological subscale: sum of severity points from questions 6, 7, 8, 11, 13
- Somatic subscale: sum of severity points from questions 1, 2, 3, 4, 5, 9, 10
- Sexual subscale: sum of severity points from questions 12, 14, 15, 16, 17
- Total score: sum of severity points from all questions from 1 to 17

Reference: Moore C, Huebler D, Zimmermann T, Heinemann LA, Saad F, Thai DM. The Aging Males' Symptoms scale (AMS) as outcome measure for treatment of androgen deficiency. Eur Urol 2004;46(1):80-7

(2) EORTC QLQ-C30

The Global health status/QoL score and each Functional scales score (physical, role, emotional, cognitive, social) will be calculated as follows. The "range" used in the calculations is the difference between the maximum possible values of the score and the minimum possible value. If more than half of the scores are missing, then the Global health status/QoL score or the Functional scales score will be treated as missing. If at least half of the scores are available, then the scores that are available will be used for the calculation.

- Global health status/QoL score: {[(average of item 29 & 30)-1]/range}*100
- Physical functioning: {1-[(average of item 1 to 5)-1]/range}*100
- Role functioning: {1-[(average of item 6 & 7)-1]/range}*100
- Emotional functioning: {1-[(average of item 21 to 24)-1]/range}*100
- Cognitive functioning: {1-[(average of item 20 & 25)-1]/range}*100
- Social functioning: {1-[(average of item 26 & 27)-1]/range}*100

Reference: Fayers PM, Aaronson NK, Bjordal K, Groenvold M, Curran D, Bottomley A, on behalf of the EORTC Quality of Life Group. *The EORTC QLQ-C30 Scoring Manual (3rd edition)*. Published by: European Organisation for Research and Treatment of Cancer, Brussels 2001.

(3) EPIC

Each of the HRQOL Domain Summary Scores (urinary, bowel, sexual, hormonal) will be calculated according to the following steps.

1) Convert score using the conversion table below.

Conversion Table Converted					
Question No.	Answer	Score			
1, 2, 3, 8, 9, 14, 20, 21, 22, 23, 26, 27, 28, 29, 32	1	0			
	2	25			
	3	50			
	4	75			
	5	100			
4	1	0			
	2	33			
	3	67			
	4	100			
5	0	100			
	1	67			
	2	33			
	3	0			
6A, 6B, 6C, 6D, 6E, 6F, 15A, 15B, 15C, 15D,	0	100			

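### AMS change in Part B is summarised only as percent change of a raw sum score, so the mean depends on item coding and leans modestly towards apparent worsening; report change from baseline

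*SAP*

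**What the plan says.** SAP 4.1.2 covers three instruments in Part B. For AMS, item (1), the output is "Descriptive statistics for the actual values and the percent change from" baseline, for the subscale and total scores, at each visit and by treatment group. For QLQ-C30, item (2), it is "Descriptive statistics for the actual values and the change from baseline of" the global and functional scores. Item (3) treats EPIC in the same way as QLQ-C30. No reason is given for the difference, and absolute AMS change is not tabulated anywhere.

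SAP Appendix 3 builds the AMS scores by plain addition: "Total score: sum of severity points from all questions from 1 to 17", and for example "Psychological subscale: sum of severity points from questions 6, 7, 8, 11, 13". The somatic and sexual subscales add 7 and 5 items. The item minimum is not subtracted and nothing is rescaled. QLQ-C30 is handled differently: "Global health status/QoL score: {[(average of item 29 & 30)-1]/range}*100". EPIC averages items already converted to a 0-100 scale. The range of an AMS item is not stated.

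The SAP glossary defines the statistics to be shown: "Descriptive statistics: number of subjects, mean, standard deviation (SD), maximum (max), minimum (min), and quartiles". Protocol 5.2.3 and 13.1.6 list quality of life among the additional endpoints and set no change metric, so the choice is made in the SAP alone.

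**The concern.** A ratio to baseline is easiest to read when zero is a fixed and meaningful point. A sum of severity points has a floor set by the coding. If items start at 1, the 17-item total cannot fall below 17. If they start at 0, a man without symptoms has a zero baseline and his percent change is undefined. In either case equal point changes become unequal percentages, and low-baseline men carry more weight in the mean.

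Higher AMS means more severe symptoms, so the distortion of the mean runs towards apparent harm. The title of the AMS reference cited in both documents concerns androgen deficiency, which is relevant to a drug that suppresses testosterone. What is at stake is how the AMS change table is read. Sample size, dose decisions and the safety conclusions do not depend on it.

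**Working it through.** **The plan's own figure.** The only design figure is that "15 subjects per group (total of 30 subjects) were established as the number of cases enabling an approximately 80% chance" of seeing an adverse event with true incidence 10%. Check: 1 - 0.9^15 = 0.794, which agrees. It has no bearing on AMS, but it supplies the group size n = 15 used below.

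**Inputs.** From the documents: sums of 17, 5, 7 and 5 items; percent change for AMS; n = 15 per group. Assumed, because the documents do not give them: items scored 1-5 (alternative 0-4); total mean 30 with SD 6, 9 or 12; correlation between baseline and follow-up 0.5 or 0.7.

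**1. Weighting.** With baseline X and follow-up Y, the planned mean is the average of 100(Y - X)/X, so each man's change is weighted by 1/X. A 5-point worsening is 5/20 = +25% from 20 and 5/50 = +10% from 50. Two men who swap, 25 to 35 and 35 to 25, have mean change 0 and mean percent change (40.0% - 28.6%)/2 = +5.7%.

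**2. Coding.** The same answers give different percentages under the two codings:

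| Score | Change | Items 1-5 | Items 0-4 |
|---|---|---|---|
| 17-item total | 7 points | 27 to 34: 7/27 = +25.9% | 10 to 17: 7/10 = +70.0% |
| 5-item subscale | 3 points | 7 to 10: 3/7 = +42.9% | 2 to 5: 3/2 = +150% |

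The absolute change is 7 or 3 points under either coding.

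**3. Expected size with no true shift.** If baseline and follow-up have the same mean m, SD s and correlation r, a second-order expansion gives an expected percent change of about 100(1 - r)(s/m)^2. Simulation (40,000 groups of 15, scores rounded and held within 17-85) gives:

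| SD | r | Approximation | Simulated mean % change | Simulated mean change (points) |
|---|---|---|---|---|
| 6 | 0.7 | 0.3 x 0.04 = 1.2% | +1.3% | 0.0 |
| 6 | 0.5 | 0.5 x 0.04 = 2.0% | +2.1% | 0.0 |
| 9 | 0.7 | 0.3 x 0.09 = 2.7% | +2.6% | 0.0 |
| 9 | 0.5 | 0.5 x 0.09 = 4.5% | +4.4% | 0.0 |
| 12 | 0.7 | 0.3 x 0.16 = 4.8% | +4.0% | 0.0 |
| 12 | 0.5 | 0.5 x 0.16 = 8.0% | +6.5% | 0.0 |

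The approximation ignores the floor at 17, which trims low baselines when the SD is 12. For 5-item subscales (assumed means 9 and 12, SD 20-40% of the mean) the simulated range is +1.4% to +8.8%.

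**4. Disagreement in sign.** With no true shift, 12% to 24% of simulated groups had a mean change of zero or better while the mean percent change was positive. With a true 5-point worsening this falls to between 0% and about 4%, and with 8 points to at most 0.5%.

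**5. What the planned median shows.** In the no-shift cases the median percent change averages only +0.1% to +0.5%.

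**The case against.** The strongest reply is that the planned tables already expose most of the problem. Quartiles are reported, the median percent change sits near zero when nothing has shifted, and actual AMS values appear at baseline and every visit. Percent change is also this SAP's usual metric (PSA, testosterone, the other hormones, bone mineral density), and for an unrescaled score it is one way of putting subscales of unequal length on a common footing. The cited AMS paper might support it; that cannot be checked from the documents. QOL here has no test, confidence interval or responder rule.

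Much of this stands, and it sets the size of the point. Two things remain. The median is still a percentage of a coding-dependent score. And visit means of actual values are not paired with the same men's baselines: Protocol 6.1 does not replace withdrawals and makes treatment after Week 48 optional, while AMS is summarised to Week 97. The other percent-change variables are physical measurements with a real zero.

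A reader might infer three stronger things that the documents do not support:

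- **That the AMS mean will have the wrong sign.** This is common only with no true shift. If AMS worsens by 5 points, sign conflict is rare.
- **That zero baselines will break the calculation.** This needs items scored from 0, and the coding is not given.
- **That absolute change would make AMS comparable in size with QLQ-C30 and EPIC.** It would not. AMS stays a raw sum with higher meaning worse, while the other two are on 0-100 scales and the QLQ-C30 functional scales run the opposite way.

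**Conclusion.** The point holds at low severity. As planned, the only within-subject summary of AMS is a percentage that depends on undocumented item coding and over-weights low-baseline men. For the total score in a group of 15 with no real change, the mean is pulled up by about 1% to 7%. This rests on assumed items 1-5, mean 30, SD 6-12 and correlation 0.5-0.7; none of these is in the documents, and other values would move the range. The larger percentages for individual men or constructed pairs show the mechanism and are not expected group results. AMS is an additional descriptive endpoint, so the consequence is confined to interpreting AMS.

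**What to change.** In SAP 4.1.2 (1), make change from baseline in AMS subscale and total scores, at each visit and by treatment group, the change summary. Keep the actual values. Percent change may stay as an optional extra column. This gives a paired summary whose value is the same whichever item origin is used and which does not over-weight low baselines. The cost is a short SAP edit and one derivation from data already collected, with no protocol amendment. The revised text should not present the three instruments as comparable in magnitude.
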